6.4 Concomitant Medications

A listing of concomitant medications will be provided for the Safety Population. Rescue medication for asthma exacerbation and antibiotic use for sinus infections will be summarized as noted above.

7 EFFICACY ANALYSES

All hypothesis tests will be performed at the 0.05 level. Analyses of the primary efficacy variables will be performed using both the ITT and PP Populations; analyses of secondary efficacy variables will be performed using the ITT population only. Summary statistics will be presented for all analyses of efficacy variables.

7.1 Primary Efficacy Analysis

The primary analysis of interest is the CFB in SNOT-22 at week 8 on the ITT population, imputed with LOCF. Between-treatment comparison will be performed using Analysis of Covariance (ANCOVA) with SNOT- 22 at baseline and treatment in the model. The p-value associated with the difference between the treatments in least squares will determine significance. Least squares (LS) means, differences in LS means and the associated p-value, corresponding standard errors, and corresponding confidence intervals will be presented in a table. To assess sensitivity, this analysis will also be performed on the CFB SNOT-22 imputed using MI (Section 5.1).

The chart below outlines the analyses to be performed on each variable. It identifies the weeks for which the analysis will be performed for the corresponding variable, population, and type of imputation.

Variable Name	Value Type	Pop	Weeks for Analysis		Sensitivity (1)
			Summary	ANCOVA	
SNOT-22	Score Value	ITT/PP	0,4,8,10		LOCF
	Score CFB	ITT/PP	0,4,8,10	4,8,10	LOCF/MI

(1) Imputation analysis outlined in Section 5.1. LOCF=Last observation carried forward, MI=Multiple Imputation

7.2 Secondary Efficacy Analyses

The analyses performed for the secondary efficacy variables will be combinations of summary statistics and ANCOVAs, using the normal approximation to the binomial (see Appendix A for details.) as appropriate, at specified visits presented in the table below.

The ANCOVA will include the corresponding value at Baseline as the only covariate with treatment. The LS means, standard error and p-values will be presented with corresponding the summary statistics.

Categorical variables will be analyzed using the normal approximation to the binomial distribution, assuming unequal variances. The p-value will be presented along with summary statistics.

The chart below outlines the analyses to be performed on each variable. It identifies the weeks in which the analysis will be performed for the variable of interest, the population, and the type of imputation.

Variable Name	Value Type	Pop	Weeks for Analysis			Imputation (2)
			Summary	ANCOVA	Binomial (1)	
SNOT-22	Score PCFB	ITT	0,4,8,10			LOCF
	Improvement(y/n)	ITT	0,4,8,10		4,8,10	NRI
SNOT-22 Subscale	Nasal Related	ITT	0,4,8,10			LOCF
	Ear and Facial	ITT	0,4,8,10			LOCF
	Quality of Life	ITT	0,4,8,10			LOCF
	Psychological	ITT	0,4,8,10			LOCF
	CFB Nasal Related	ITT	0,4,8,10			LOCF
	CFB Ear and Facial	ITT	0,4,8,10	4,8,10		LOCF
	CFB Quality of Life	ITT	0,4,8,10	4,8,10		LOCF
	CFB Psychological	ITT	0,4,8,10	4,8,10		LOCF
	22 Questions	ITT	0,4,8,10			LOCF
FEV1	Value	ITT	0,4,8,10			LOCF
	CFB	ITT	0,4,8,10	4,8,10		LOCF
PNIFR	Value	ITT	0,4,8,10			LOCF
	CFB	ITT	0,4,8,10	4,8,10		LOCF
UPSIT	Value	ITT	0,4,8,10			LOCF
	CFB	ITT	0,4,8,10	4,8,10		LOCF
FeNO	Value	ITT	0,4,8,10			LOCF
	CFB	ITT	0,4,8,10	4,8,10		LOCF
ACQ	Value	ITT	0,4,8,10			LOCF
	CFB	ITT	0,4,8,10	4,8,10		LOCF
	Improvement (y/n)	ITT	0,4,8,10		4,8,10	NRI

(1) Normal approximation to the Binomial
 (2) Imputation analysis outlined in Section 5.1. NRI=Non responder imputation, LOCF=Last observation carried forward

Variable Name	Value Type	Pop	Analysis			
			Summary	ANCOVA	Binomial (1)	Imputation (2)
TNSS AM/PM	Visit Score	ITT	4,8,10			LOCF
	CFB Visit score	ITT	4,8,10	4,8,10		LOCF
Asthma	Reports	ITT	0,4,8,10			LOCF
	CFB Reports	ITT	0,4,8,10	4,8,10		LOCF
	Max Severity	ITT	0,4,8,10			LOCF
	Rescue report	ITT	0,4,8,10			LOCF
	CFB rescue report	ITT	0,4,8,10	4,8,10		LOCF
Sinusitis	Reports	ITT	0,4,8,10			LOCF
	CFB Reports	ITT	0,4,8,10	4,8,10		LOCF
	Max Severity	ITT	0,4,8,10			LOCF
	Antibiotic report	ITT	0,4,8,10	4,8,10		LOCF
	CFB Antibiotic report	ITT	0,4,8,10			LOCF
Plasma	ScD10L	ITT	0,4,8,10			LOCF
	Sp_selection	ITT	0,4,8,10			LOCF
Bio-Markers	LTE4	ITT	0,4,8,10			LOCF
	PGD-M	ITT	0,4,8,10			LOCF
	TX-M	ITT	0,4,8,10			LOCF
	F2 Isoprostanes	ITT	0,4,8,10			LOCF
	LTb4	ITT	0,4,8,10			LOCF
	SAM-Eicosanoids PGD2	ITT	0,4,8,10			LOCF
	SAM-Eicosanoids PXA2	ITT	0,4,8,10			LOCF
	SAM-Eicosanoids F2 Isoprostanes	ITT	0,4,8,10			LOCF

(1) Normal approximation to the Binomial
 (2) Imputation analysis outlined in Section 5.1. NRI=Non responder imputation, LOCF=Last observation carried forward

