### 11.6.3.2 Analysis of secondary endpoints

CFB in ACQ-7 and CFB in TNSS at Week 8 will be analyzed using ANCOVA, with the corresponding value at Baseline included as the only covariate. These variables, as well as CFB in SNOT-22, at Week 4 will also be analyzed as ancillary analyses.

Analyses of CFB for other continuous efficacy variables will be performed at Weeks 4 and 8 in the same manner using ANCOVA with the corresponding value at Baseline included as the only covariate.

Any improvement in SNOT-22, ACQ-7, and TNSS (Yes or No) at Weeks 4 and 8 will be analyzed using the normal approximation to the binomial distribution, assuming unequal variances.

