4.5 Sample Size Determination

Thirty-eight subjects per group will provide 90% power for the comparison of ifetroban and placebo with respect to the change from baseline in SNOT-22 scores at Week 8 (two-sided, level 0.05), assuming a common standard deviation of 16 and a true difference is 12.

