10 APPENDIX

Appendix A

Normal Approximation to the Binomial Distribution Test

Let n_1 and n_p denote the sample sizes and let m_1 and m_p denote the number of responses for Ifetroban (200mg/day), and Placebo, respectively. Furthermore, let $r_1 = m_1/n_1$, and $r_p = m_p/n_p$, denote the sample proportions for Ifetroban (200mg/day) and Placebo, respectively. Note that 'r' is used to denote proportions instead of the standard 'p' because p is being used to denote the p-value.

let

$$Z_{1p} = (r_1 - r_p)/s_{1p}$$

where

$$s_{1p} = \{r_1(1-r_1)/n_1 + r_p(1-r_p)/n_p\}^{1/2}.$$

The corresponding p-value is $p=1-\Phi(Z_{1p})$ where Φ is the standard normal distribution function and is calculated using the *PROBNORM* SAS function in the data step.

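### The ancillary responder tests leave out the baseline score and use an unpooled standard error: a slight excess over the 0.05 level, and a modest power loss that depends on an unstated correlation

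*SAP*

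**What the plan says.** - **Method.** SAP 7.2: "Categorical variables will be analyzed using the normal approximation to the binomial distribution, assuming unequal variances". Protocol 11.6.3.2 specifies the same test: improvement "will be analyzed using the normal approximation to the binomial distribution, assuming unequal variances". The protocol synopsis calls these responder analyses ancillary.
- **Formula.** SAP Appendix A divides the difference in sample proportions by a standard error built from the two separate proportions. No covariate enters. Its p-value is an upper-tail probability, so it is one-sided as written. That is a separate matter; the sizes below treat the test as two-sided, as in the sample-size text.
- **Responder.** SAP 4.6 counts any fall from baseline (change below 0) as improvement. SAP 5.1 counts missing responses as failures. The SAP 7.2 tables schedule the test for SNOT-22 and ACQ-7 at Weeks 4, 8 and 10. The protocol also names TNSS, but the SAP tables do not.
- **Reporting.** SAP 7.2: "The p-value will be presented along with summary statistics". SAP 5 defines the summary for categorical data as n and %. No confidence interval is named.
- **Level.** SAP 7: "All hypothesis tests will be performed at the 0.05 level".
- **Contrast.** The primary ANCOVA (SAP 7.1) and the secondary ANCOVAs (SAP 7.2) adjust for the baseline value of the variable analysed. The primary analysis also reports differences and confidence intervals.

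**The concern.** Two features of the test are separate and should be kept apart.

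1. **Standard error.** Under the null hypothesis the two response rates are equal, yet the standard error does not use that. With equal arms the unpooled standard error is never larger than the pooled one, so Z is never smaller. The actual level may then exceed 0.05.
2. **Baseline omitted.** The responder is defined by change from baseline. If change is correlated with baseline, leaving baseline out of the model wastes information that the trial already collects.

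At stake are the level and power of a set of ancillary tests, and whether the reader gets an effect size with its uncertainty.

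**Working it through.** **Inputs from the documents.** 38 per arm, SD 16, difference 12, two-sided 0.05 (SAP 4.5); responder = change below 0 (SAP 4.6); the Appendix A formula.

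**Assumed, because the documents do not give them.** Response rates, the number analysed, the placebo mean change, and the correlation of baseline with Week 8 or with change. Scores are taken as normal.

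**1. The plan's own figure.** SAP 4.5: "Thirty-eight subjects per group will provide 90% power for the comparison of ifetroban and placebo", "assuming a common standard deviation of 16 and a true difference is 12". Standard error = 16 × √(2/38) = 3.671; 12/3.671 = 3.269; power = Φ(3.269 − 1.960) = Φ(1.309) = 90.5%. A noncentral t gives 89.7%. The stated 90% is reproduced. It applies to the continuous endpoint; the documents give no size or power for the responder test.

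**2. Size, by approximation.** With n per arm and d = r1 − rp:
- unpooled variance = [r1(1 − r1) + rp(1 − rp)]/n
- pooled variance = 2r̄(1 − r̄)/n, where r̄ is the mean of r1 and rp
- pooled minus unpooled = d²/(2n)

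Hence Zpooled² = Zunpooled²/(1 + Zunpooled²/(2n)). At n = 38 and Zunpooled = 1.960: 3.8415/(1 + 3.8415/76) = 3.657, so Zpooled = 1.912. The planned test is a pooled test with critical value 1.912 instead of 1.960, a nominal level of 2 × (1 − Φ(1.912)) = 5.6%.

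**3. Size, exact.** Sum the two binomial distributions over all outcomes with |Z| > 1.960, at a common response rate:

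| Arms | Common rate | Unpooled (planned): mean, max | Pooled: mean, max |
|---|---|---|---|
| 38 v 38 | 0.05–0.95 | 5.5%, 5.9% | 5.1%, 5.8% |
| 37 v 38 | 0.30–0.90 | 5.9%, 6.4% | 5.6%, 6.4% |
| all pairs 33–38 | 0.30–0.90 | 5.8%, 7.2% | 5.1%, 6.4% |

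The 7.2% occurs at 35 v 35 with a rate of 0.50; the pooled test has 4.3% there. The unpooled size exceeds 5.5% in 79% of the settings in the last row.

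**4. Power at one set of assumptions.** Take a placebo mean change of -6. Response rates are Φ(6/16) = 64.6% on placebo and Φ(18/16) = 87.0% on ifetroban. At 38 per arm, exact power is 66.7% for the planned unpooled test and 64.2% for the pooled test. If baseline and Week 8 have equal SDs and correlation r, the baseline-change correlation is −√((1 − r)/2): -0.55, -0.50 and -0.45 for r = 0.4, 0.5 and 0.6. In 5,000 simulated trials per setting, the likelihood-ratio test from logistic regression with baseline has 72%, 71% and 71% power. The planned test has 67%, 66% and 67% in the same trials. Before rounding, the gains are 5.8, 4.6 and 3.5 points. The null size of the adjusted test is 5.3% to 5.8%, against 5.3% to 5.9% for the planned test.

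**5. Range over the unknown correlation.** 6,000 trials per setting, placebo change 0, -4, -8 and -12; gain of the adjusted test over the planned one:

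| Baseline-change correlation | Gain in power (points) |
|---|---|
| 0 | -2 to 0 |
| -0.3 | 1 to 2 |
| -0.5 | 4 to 6 |
| -0.6 | 8 to 10 |
| -0.7 | 12 to 14 |

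Simulation error is about 0.6 points per power figure.

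**The case against.** The case for leaving the plan alone is fair in several respects.

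- **Low consequence.** The analyses are ancillary, and SAP 5.4 makes no multiplicity adjustment. The primary inference is a baseline-adjusted ANCOVA with confidence intervals. This stands.
- **The 7.2% is not the plan's error rate.** A reader might take it so. It needs 35 v 35 and a 50% rate. Missing responses count as failures, so most dropouts stay in the denominator. An arm shrinks only through subjects who were never treated or have no post-baseline SNOT-22. Falling to 33 would take 5 of 38, or 13%, and the documents give no such rate. On the other hand, 76 randomised leaves no margin above 38 per arm, and early terminations are not replaced (Protocol 9.1), so arms slightly below 38 are possible.
- **The power loss is easily overstated.** Against a pooled test, the adjusted model appears to gain roughly 6 to 9 points, depending on the simulation run. The SAP does not use a pooled test. Against the planned test the gain is 3 to 6 points at the same assumptions. Nor does the unpooled variance cost power: it has slightly more, because it rejects more readily.
- **The remedy does not restore the level.** The adjusted test's null size is also about 5% to 6% across the runs, and the pooled test reaches 6.4% at 37 v 38. This stands.
- **Two broader readings fail.** Not every ANCOVA adjusts for the baseline of the variable analysed: most subgroup models in SAP 7.3 carry another covariate and no baseline SNOT-22. And more than a p-value is reported: n and % let a reader form the difference. Only its confidence interval is missing.

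What survives is a cheap gain in precision, and the missing interval.

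**Conclusion.** The point holds in a limited form. As a two-sided test, the planned statistic runs at about 5.5% at 38 per arm (maximum 5.9%), and at about 5.8% on average if arms fall between 33 and 38. That is a real but small excess. Leaving out baseline costs about 3 to 6 points of power if the placebo change is -6 and the baseline/Week 8 correlation is 0.4 to 0.6. The documents support neither assumption, and the range runs from about -2 points (no baseline-change correlation) to +14 (correlation -0.7). The loss comes from omitting baseline, not from the unpooled variance. The change is worth making for precision, for consistency with the primary and secondary ANCOVAs, and for an effect estimate with an interval. It should not be presented as a repair of type I error, and it has no bearing on the primary result.

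**What to change.** - **SAP 7.2 and Appendix A.** Replace the Z test by logistic regression with treatment and the corresponding baseline score, tested by a two-sided likelihood-ratio test. Name that test explicitly: at high response rates the Wald test loses much power (44% v 60% in the runs with placebo change -12 and correlation -0.5).
- **Reporting.** Beside the planned n and %, give the standardised difference in response rates (model predictions averaged over all ITT subjects under each treatment) with a 95% CI.
- **Consistency.** Make the same change in Protocol 11.6.3.2 or list it in SAP section 9. SAP section 1 already allows revision before unblinded analyses.
- **If an unadjusted test is kept.** Use the pooled (score) statistic. It averages 5.1% at 38 v 38, can reach 5.8% to 6.4% at some rates and arm sizes, and gives up about 2 to 3 points of power against the planned test.

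Cost: some SAP wording and a few lines of code. Some p-values will become slightly larger, and if baseline turns out to be uncorrelated with change, up to about 2 points of power are lost.

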7.3 Subgroup Analyses

To assess the consistency of treatment effects across the subgroup levels, and to examine baseline biomarkers for their potential value to predict treatment response, exploratory analyses will be conducted for CFB SNOT-22 (imputed using LOCF) for the variables below.

Each covariate will be used in separate regression models for CFB SNOT-22, along with the treatment and interaction. The p-value for treatment and the interaction will be presented. Additional ad-hoc exploratory analyses may be provided based on the results of these analyses; any additional analyses will be presented in a separate report.

Covariate	Pop	Analysis		
		Summary	ANCOVA	ANOVA
Age	ITT		4,8,10	
Gender	ITT			4,8,10
Site	ITT			4,8,10
Race	ITT			4,8,10
Baseline SNOT-22	ITT		4,8,10	
Baseline TNSS	ITT		4,8,10	
Baseline ACQ-7	ITT		4,8,10	
LTE4	ITT	8	8	
PGD-M	ITT	8	8	
TX-M	ITT	8	8	
F2 Isoprostanes	ITT	8	8	
LtBct	ITT	8	8	
SAM-Eicosanoids PGD2	ITT	8	8	
SAM-Eicosanoids PXA2	ITT	8	8	
SAM-Eicosanoids F2 Isoprostanes	ITT	8	8	

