5.1 Handling of Dropouts or Missing Data

Missing efficacy data which are not retrievable through queries will be imputed.

NRI

Binary response efficacy variables will be imputed by treating the missing data as a failure, ie, non-responder imputation (NRI). A response variable that is calculated from a continuous variable will only be imputed using NRI, not from the imputed continuous variable.

LOCF

Missing data for continuous efficacy variables with at least one post-baseline measurement will be imputed using Last Observation Carried Forward (LOCF). Any calculated continuous variable will be imputed after its creation.

If the baseline value is missing for any variable, then the last screening value will be used.

MI

Multiple imputation (MI) will be provided as a sensitivity analysis for the primary efficacy variable (SNOT-22 Score CFB) only. Six imputations will be calculated from PROC MI. Week 8 will be imputed using week 0 and week 4 by treatment by treatment. The analysis will be performed on the 6 imputed sets which will provide 6 estimates of LS means from separate analyses of ANCOVAs (see Section 7.1).

```
proc mi data=thedata out=outds n impute=6 seed=310
min=(-110 -110 -110 -110 -110 -110)
max=(110 110 110 110 110 110)
round=(1 1 1 1 1 1)
minmaxiter=100
noprint;
by trt;
var SNOT22BASE SNOT22CFB4 SNOT22CFB8;
run;
```

where SNOT22BASE is the baseline SNOT22 score and, SNOT22CFB4 and SNOT22CFB8 are the SNOT-22 Score values at Weeks 4 and 8, respectively.

The seed specified above will be used for development, but may be changed prior to unblinding; any such change will be documented. If convergence is not achieved with minmaxiter=100, then increase the number of iterations to 500. The properties of this approach, including convergence and collinearity, will be assessed prior to unblinding and may be adjusted to improve the operating characteristics.

After calculating the LS means of the two treatments and the estimated treatment difference and associated standard error from the ANCOVA, the 6 estimates can be placed in PROC MI analyze.

Code to obtain a single estimate of the treatment LS means and standard error.

```
proc mianalyze=thedata ; **Data output from proc mixed;  
by trt;  
modeleffects estimate; ***estimate of lsmeans for 6 sets;  
stderr stderr; *** estimate of standard error for 6 sets;  
run;
```

Code to obtain a single estimate p-value for the treatment difference.

```

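### SAP 7.3 reports a treatment p-value from interaction models without saying at which covariate value the effect is tested, and 14 of the 15 models omit baseline SNOT-22

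*SAP*

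**What the plan says.** SAP 7.3 describes the subgroup work as exploratory: "exploratory analyses will be conducted for CFB SNOT-22 (imputed using LOCF) for the variables below". On the model it says: "Each covariate will be used in separate regression models for CFB SNOT-22, along with the treatment and interaction". On output it says: "The p-value for treatment and the interaction will be presented".

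The table in that section lists 15 covariates. Twelve are in the ANCOVA column and so are treated as continuous: age, baseline SNOT-22, baseline TNSS, baseline ACQ-7 and eight biomarkers. Gender, site and race are in the ANOVA column. Nothing is said about centring, a reference covariate value, the type of test, or further adjustment.

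The primary model in SAP 7.1 is an ANCOVA "with SNOT- 22 at baseline and treatment in the model", with no interaction term. Protocol 11.3 leaves the details of the subgroup analyses to the SAP.

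**The concern.** Once a treatment-by-covariate interaction is in the model, there is no single treatment effect to test. The treatment term is the effect at the covariate value coded as zero. With raw values, that is the effect at age 0 or at a SNOT-22 score of 0. SAP 4.2 admits only subjects aged at least 18 with a SNOT-22 of at least 20 at entry, so for these two covariates the p-value would rest on extrapolation beyond the subjects recruited and would carry a much larger standard error.

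The risk is one of misreading. A real and uniform benefit could appear in some rows as a non-significant treatment p-value beside a significant primary result. SAP 7.3 also allows further ad hoc analyses prompted by these results.

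A second, smaller matter is that only the model for baseline SNOT-22 itself contains that score. The other 14 drop the covariate that the primary analysis adjusts for. They are therefore less precise than they could be, and less directly comparable with the primary estimate.

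**Working it through.** **Inputs from the documents.** SAP 4.5: 38 per group, SD 16, true difference 12, "two-sided, level 0.05", 90% power. SAP 4.2: age at least 18, SNOT-22 at least 20. SAP 7.3: 12 continuous and 3 categorical covariates.

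**The plan's own figure.** SE0 = 16 × √(2/38) = 3.67, and 12/3.67 = 3.27. The noncentral t distribution with 74 df gives power 0.897, and the normal approximation gives 0.905. The stated 90% is reproduced.

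**How many p-values.** Four continuous covariates at Weeks 4, 8 and 10, plus eight biomarkers at Week 8 only: 4 × 3 + 8 = 20 treatment p-values from models with a continuous covariate. The categorical covariates add 3 × 3 = 9.

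**Formula.** With a covariate balanced across arms, the treatment term has SE ≈ SE0 at the covariate mean and SE ≈ SE0 × √(1 + (mean/SD)²) at covariate = 0. For example, age with mean 45 and SD 15 gives √(1 + 9) = 3.16 and an SE of 3.67 × 3.16 = 11.6.

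**Results.** Every mean, SD and coefficient of variation (CV) below is an assumption, because the documents give none. Power is for a constant 12-point effect, with 72 df and a residual SD of 16.

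| Covariate | Assumed mean/SD | SE factor at 0 | SE | Power |
|---|---|---|---|---|
| Any, centred | – | 1.0 | 3.67 | 0.90 |
| Age | 45/15 to 50/10 | 3.2 to 5.1 | 11.6 to 18.7 | 0.18 to 0.10 |
| Baseline SNOT-22 | 40/20 to 50/15 | 2.2 to 3.5 | 8.2 to 12.8 | 0.30 to 0.15 |
| Baseline TNSS | 4/3 to 6/2 | 1.7 to 3.2 | 6.1 to 11.6 | 0.49 to 0.18 |
| Baseline ACQ-7 | 1/1 to 2/0.8 | 1.4 to 2.7 | 5.2 to 9.9 | 0.63 to 0.22 |
| Biomarker | CV 2 to CV 1 | 1.1 to 1.4 | 4.1 to 5.2 | 0.82 to 0.63 |
| Biomarker | CV 0.5 | 2.2 | 8.2 | 0.30 |

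The SNOT-22 row is slightly pessimistic, because that model already contains the baseline score. At an assumed 45/18, power is 0.22 with a residual SD of 16. It rises to about 0.24-0.32 if baseline correlates 0.3-0.6 with CFB.

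**Simulation check** (3,000 trials of 76 subjects). Age drawn from 48/13 and cut at 18: mean SE 15.1 raw against 3.7 centred, rejection rate 13% against 90%. SNOT-22 drawn from 45/18 and cut at 20 (realised mean 48, SD 15.5): SE 12.2 against 3.7, rejection 17% against 90%. If the effect is instead proportional to baseline SNOT-22 and averages 12, the raw test rejects in about 6% of trials and the centred one in about 89%.

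**Leaving out baseline SNOT-22.** If its correlation with CFB is ρ, adding it multiplies the SE by √(1 − ρ²).
- ρ = 0.3: 3.67 × 0.954 = 3.50, a 5% cut.
- ρ = 0.5: 3.67 × 0.866 = 3.18, a 13% cut.
- ρ = 0.6: 3.67 × 0.80 = 2.94, a 20% cut.

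Seen from the other side, omission raises the SE by about 5%, 15% and 25%.

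**The case against.** The strongest reply is that the SAP never says the covariates will be entered raw. A programmer might centre them, or take the treatment contrast at the covariate mean. That is correct. A reader might infer that the plan prescribes an uncentred model, but the text does not support this. What it supports is that the tested quantity is unspecified, with the effect at zero as what a literal fit would give. The only software hint, the note "Data output from proc mixed" in SAP 5.1, concerns the multiple-imputation version of the primary analysis and does not settle the matter. SAP 1 provides for review of the document and its table shells before unblinding. That is a natural moment to close the gap, but it does not itself close it.

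A reader might also infer that the treatment p-values throughout these tables are meaningless. That goes too far. Gender, site and race have no covariate-equals-zero problem, since the usual test for categorical factors averages over levels. Zero is an attainable score on ACQ-7 and TNSS, and for highly variable biomarkers the inflation may be slight. The argument about eligible range applies only to age and SNOT-22.

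The objection is also right on consequences. The stated aims, consistency across subgroups and prediction by biomarkers, rest on the interaction test, which centring leaves unchanged. SAP 7.1 makes the primary ANCOVA p-value decisive, so a subgroup main-effect p-value cannot overturn it. Finally, omitting baseline SNOT-22 does not bias a randomised comparison and explains little of the possible SE inflation, nearly all of which comes from the reference value.

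**Conclusion.** The point holds as a minor gap in specification. SAP 7.3 promises a treatment p-value without defining the effect that it tests. If covariates are entered raw, the test for age and for baseline SNOT-22 has roughly 10-18% and 15-30% power against a uniform 12-point benefit (somewhat higher for SNOT-22 if baseline explains part of the variance), where a centred model has about 90%. For ACQ-7 the range is about 22-63%. These figures depend on assumed means and SDs and on raw entry, neither of which the documents state. The entry score is taken at screening, so a Week 0 score below 20 is possible, but 0 remains far from the recruited range.

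The omission of baseline SNOT-22 from 14 of the 15 models is certain on the text as written. It is a loss of precision only: adding the score would cut the SE by about 5-20% if its correlation with CFB is 0.3-0.6.

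The documents do not support reading this as a threat to the trial's main conclusion. The primary model has no interaction term, and the subgroup analyses are labelled exploratory.

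**What to change.** Amend SAP 7.3 before unblinding:

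- Add baseline SNOT-22 as a covariate in every subgroup model.
- Centre each continuous covariate at its pooled mean, or drop the treatment main-effect p-value from these tables.
- Report the interaction estimate with a 95% confidence interval, and treatment effects with confidence intervals at stated covariate values or factor levels.
- As a clarification only, label the biomarker rows as Week 0 values. The text above the table already refers to biomarkers at baseline, but the rows themselves do not carry the label.

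The cost is a few sentences in the SAP and a few lines of code. No new data are needed, and the primary analysis and the sample size do not change.
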